10.2.4 Coronary artery assessment subgroup

Circumflex artery has a close anatomical relationship with LAA and both Watchman/FLX and Amulet devices are implanted in a region adjacent to that vessel. Our group has recently observed some cases of subocclusive stenosis of proximal circumflex artery occurred few years after LAAC. In both cases, despite of the close proximity between the LAAC device and the stenosis, no signs of external compression have been detected. Therefore, we speculated that LAAC could have accelerated the local inflammatory process and the progression of coronary plaque burden in the circumflex artery compared to other coronary arteries. In order to test this hypothesis (with the aim to detect some trend), we will use the serial CCTAs, to assess the difference between the circumflex artery and the remaining coronary arteries in terms of coronary plaque burden progression after 1 year. The coronary plaque burden progression is defined as the absolute annual increase in total, calcified, and noncalcified plaque volume; therefore

it consists of the difference between of total plaque volume (in particular the non calcified component) measured by 13 month CCTA and that measured by the preprocedural or 45 day CCTA.

In this subgroup analysis will be included all the patients with at least one of the first two CCTAs and the third CCTA with a sufficient images quality (as evaluated by the ICL) to assess coronary plaque burden. The use of nitrates and betablocker is aimed at obtaining CCTA images suitable not only for LAA patency but also for coronary artery disease assessment.²³ Images reconstruction will be optimized using the most suitable cardiac cycle phase (i.e. diastole at 70-80% of the R-R interval).

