6. STUDY DESIGN

6.1 General study design and justification of design

This will be a multicentre, open-label, prospective, randomized study in patients with AF and an indication for anticoagulant therapy with high bleeding risk, that agree to the LAAC procedure. Patients will be submitted to a screening protocol in a period not greater than 90 days before procedure, including medical and drug history, physical examination, 12-lead ECG, CCTA (as per standard of care) and TEE if clinically indicated.

Once the patient is judged eligible and the informed consent has been signed, the patient will be randomly assigned in a 1:1 to receive a LAAC with Amplatzer Amulet or Watchman/FLX device. In the event that the patient is randomized to the Watchman/FLX arm, the operator will be able to choose, on the basis of clinical reasons, if to implant Watchman or the new generation Watchman FLX (if available in the center).

Sizing device and implantation will be performed according to common practice guidelines⁵ (and so based on both preprocedural CCTA and intraprocedural TEE-angiography images). Furthermore, as recommended by the recent consensus document,⁵ the first operator will be able to choose if use intracardiac echocardiography (ICE) instead of TEE to guide the procedure, on condition that a TEE evaluation is performed within 2 days before the procedure (in order to exclude LAA thrombus, to confirm the LAA suitability for both devices and to make the device sizing). Angiography at the end of the procedure is recommended to assess PDL. In case of concomitant procedure during LAAC, it will be reported separately in term of duration time, contrast dose and x-ray dose.

At the end of procedure, a measure of PDL must be provided.

A transthoracic echocardiogram is encouraged (but not mandatory) before the hospital discharge in order to detect pericardial effusion.

All patients randomly allocated to the Watchman/FLX or Amulet arm will receive acetylsalicylic acid (ASA) and clopidogrel or (N)OAC (at discretion of the treating physician and according to the bleeding risk, stroke risk as well as based on post-procedural TEE evaluation) for 45 days and then will undergo TEE assessment (as well as CCTA):

- If a residual peri-device leak flow at 45 days > 5 mm or a intra-cardiac thrombus is detected, a therapy with ASA and (N)OAC could be considered up a sequential TEE evaluation at 6 months.

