- Assessment of SAE and AESI as defined in 11.1 and Appendix 1
- 12 lead ECG
- TEE will be performed at 45 days. TEE could be repeated at 6 and 13 months after procedure if clinically indicated (in case of an intra-cardiac thrombus or/and a PDL >5 mm are revealed at 45 days) according to current standard of care
- CCTA at 45 days and at 13 months after procedure will be performed as study specific interventions.

In the event of pandemic or any other condition for which the participation to follow-up visits would put at risk the health of the patients and/or of the medical staff, the hospital visits will be replaced by phone call. Furthermore, the performance of imaging follow-up outside of protocol temporal window will be allowed.

If a phone call is performed instead of an hospital visit, the following data will be collected:

- Vital status
- Assessment and reporting of adverse clinical events as defined in 9.1.8 and Appendix 1
- Assessment and reporting of SAEs and AESI
- Assessment and reporting of pharmacotherapy, and additional interventions received since last contact.

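### Coronary plaque progression (protocol 10.2.4) is labelled an annual increase but computed as a difference not divided by elapsed time, over in-window intervals of 313 to 515 days

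*Combined protocol and SAP*

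**What the plan says.** Protocol section 10.2.4 plans to use the serial CCTAs to compare the circumflex artery with the remaining coronary arteries "in terms of coronary plaque burden progression after 1 year". The measure is defined in two steps. First comes the label: "The coronary plaque burden progression is defined as the absolute annual increase in total, calcified, and noncalcified plaque volume". Then, as a consequence of that label, comes the computation: "it consists of the difference between of total plaque volume (in particular the non calcified component) measured by 13 month CCTA". The volume to be subtracted may come from either early scan, the one before the procedure or the one at 45 days.

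Patients enter the analysis if they have "at least one of the first two CCTAs and the third CCTA with a sufficient images quality". No preference is given when both early scans are readable.

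The timing comes from elsewhere in the protocol. Section 6.1 says: "Patients will be submitted to a screening protocol in a period not greater than 90 days before procedure", and lists the CCTA among the screening procedures. The study schedule puts enrolment at day -90 to 0, the 45-day visit at 45±7 days and the 13-month visit at 395±30 days. For a pandemic or a similar condition, section 9.1.4 adds that "the performance of imaging follow-up outside of protocol temporal window will be allowed", and gives no limit.

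The SAP has no section on this analysis.

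**The concern.** An annual increase is a rate. A difference between two volumes equals that rate only when the scans are one year apart, and the schedule does not make them so. Two patients with the same true rate of progression would get different values because they were scanned at different times, or because a different early scan was used.

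Three things are at stake:

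- **The reported size.** Any value published as an increase per year would be mis-scaled.
- **Comparability and weight.** Under a constant rate, a patient with a long interval contributes a larger difference, and so weighs more in an average, than a patient with a short one.
- **Choice of baseline.** With no rule for patients who have both early scans, the choice could be made after the volumes are known.

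**Working it through.** The documents give no numeric progression value, so there is no figure of the plan's own to reproduce. The check is on the definition.

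**Inputs (protocol study schedule; section 6.1 for the screening window)**

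- Preprocedural CCTA: day -90 to day 0.
- 45-day CCTA: 45 - 7 = day 38 to 45 + 7 = day 52.
- 13-month CCTA: 395 - 30 = day 365 to 395 + 30 = day 425.

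**Formulas**

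- Interval = day of the 13-month scan minus day of the baseline scan.
- Error of the undivided difference, read as an annual increase = interval / 365.25 - 1. This assumes linear plaque growth, which the documents do not state.
- Multiplier that restores a per-year value = 365.25 / interval.

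**Results**

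| Baseline scan | Timing | Interval (days) | Error as an annual value | Multiplier |
|---|---|---|---|---|
| 45-day | shortest | 365 - 52 = 313 | -14.3% | 1.167 |
| 45-day | nominal | 395 - 45 = 350 | -4.2% | 1.044 |
| 45-day | longest | 425 - 38 = 387 | +6.0% | 0.944 |
| Preprocedural | shortest | 365 - 0 = 365 | -0.1% | 1.001 |
| Preprocedural | day 0, 13-month scan on day 395 | 395 - 0 = 395 | +8.1% | 0.925 |
| Preprocedural | day -90, 13-month scan on day 395 | 395 + 90 = 485 | +32.8% | 0.753 |
| Preprocedural | longest | 425 + 90 = 515 | +41.0% | 0.709 |

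The in-window spread is 515 / 313 = 1.65-fold. The preprocedural scan has no nominal day within its window, so +8% applies only to a scan on day 0. For illustration, assume a scan at mid-window, day -45, and a 13-month scan on day 395. The interval is 440 days and the error is 440 / 365.25 - 1 = +20%. Against the nominal 45-day baseline, the same rate then gives values 440 / 350 = 1.26 times apart.

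**Effect on the vessel contrast.** Suppose one scan pair, T years apart, serves all vessels of a patient, and let r be the true rate. The contrast is (r for circumflex - r for other arteries) × T. It is zero when the rates are equal, and it keeps its sign when they differ, whatever T is. Only its size scales with T.

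**The case against.** The case on the other side has five parts.

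1. **There is no wrong number in the plan.** A reader might infer that the plan states an annual figure that is about 40% off. It does not. The fault is in a definition and would pass to any value later reported as annual.

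2. **The 41% is a corner case.** It needs a preprocedural scan on day -90 and a 13-month scan on day 425 in the same patient, plus linear growth. Nominal timing gives -4% to +8%. This stands, although 41% is not a ceiling if out-of-window imaging is used.

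3. **The main contrast is within patient.** A reader might infer that uneven intervals could create a spurious circumflex effect or swamp a real one. With a shared scan pair they cannot create one. The added noise is also small. Assume uniform timing within windows, half the patients on each baseline, intervals independent of rates, and a mean contrast of 0.5 SD. The interval then has a mean of about 395 days and an SD of about 52 (CV about 13%), and the SD of the contrast rises by only about 1%. This stands, with the caveat that section 10.2.4 does not say in words that one scan pair is used for all vessels.

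4. **The analysis carries little weight.** Section 10.2 places it outside the study endpoints, and section 10.2.4 seeks only a trend. It does not compare the randomised arms and has no power claim. This stands and limits the importance of the point.

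5. **The label could be read as a unit**, with the next clause merely naming the scans to subtract. This is weaker: the text presents the difference as what the measure consists of, and neither document describes a division.

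A reader might also infer that the preprocedural scan is the right baseline. The documents do not settle that. The hypothesis is that closure accelerates plaque growth. A preprocedural baseline can include up to 90 days without a device, while a 45-day baseline misses the first 38 to 52 days with one.

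**Conclusion.** The point holds as a definition that does not match its label. As written, section 10.2.4 yields a mis-scaled annual value: about -4% to +8% at nominal timing and -14% to +41% at the window extremes, with more possible outside the windows. These percentages rest on the protocol's own windows and on linear growth. The null and the sign of the circumflex contrast survive if one scan pair serves all vessels. Its size per year does not, and long-interval patients weigh more.

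The importance is low, because the analysis is exploratory. The trial's endpoints and sample size are not touched.

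**What to change.** In section 10.2.4, define progression as

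(13-month volume - baseline volume) / (days between the two scans / 365.25),

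and add two rules:

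- The same scan pair is used for all vessels of a patient.
- One baseline rule, fixed before the volumes are read, applies when both early scans are readable. The other baseline serves as a sensitivity analysis. The rule should be chosen with the exposure trade-off in mind, because annualising does not remove the difference in the period each baseline covers.

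A simpler alternative is to drop the word annual and report the intervals with the raw differences.

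The cost is a few sentences, with no change to conduct. The date of each scan used, including the preprocedural one, must be in the analysis data. Protocol section 13.2 lists visit dates as source data, section 13.1 has CCTA copies stored at the main site, and SAP section 6.2.3 already uses the delay of the 45-day CCTA in days. No section names the date of the preprocedural scan as a data field, so this needs to be confirmed.

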11. SAFETY REPORTING

During the entire duration of the study, all serious adverse events (SAEs) and Adverse Events of special interest (AESI) are collected, fully investigated and documented in source documents and electronic case report forms (eCRF). The software platform selected for this study is ICE-Advice Pharma. Study duration encompassed the time from when the participant is randomized until the last protocol-specific procedure has been completed, including a safety follow-up period.

11.1 Definitions

An **Adverse Event (AE)** is any untoward medical occurrence in a patient or a clinical investigation participant administered a pharmaceutical/device product and which does not necessarily have a causal relationship with the study procedure. An AE can therefore be any unfavourable and unintended sign (including an abnormal laboratory finding), symptom, or disease temporally associated with the use of a device (investigational) product, whether or not related to the device (investigational) product. [ICH E6 1.2]

The AESI are the clinical endpoints of the study (see the list and/or any AEs potentially related to them: overall and CV death, cerebrovascular events (including possible events like fall, syncope, headaches, blurred vision, etc.), cardiovascular events (including possible events like hypotension, myocardial infarction, chest pain, unstable angina), bleeding events (including anemization without overt bleeding); procedure-related complications (any AE occurred within 7 days after LAAC and potentially related to the procedure). All the AESI will be evaluated by the CEC and adjudicated as clinical endpoints of the study according the definitions mentioned in Appendix 1.

A **Serious Adverse Event (SAE)** is classified as any untoward medical occurrence that:

- Results in death,
- Is life-threatening,
- Requires in-patient hospitalization or prolongation of existing hospitalisation,
- Results in persistent or significant disability/incapacity.

In addition, important medical events that may not be immediately life-threatening or result in death, or require hospitalisation, but may jeopardise the patient or may require intervention to prevent one of the other outcomes listed above should also usually be considered serious. [ICH E2A]

11.2 Reporting of serious adverse events (SAE) and other safety related events

Adverse events (SAE and AESI) reporting will start once the patient is considered fully enrolled for the study (after randomization).

All SAEs must be reported immediately and within a maximum of 24 hours of awareness to the Sponsor of the study. SAEs should be reported to the Sponsor using the eCRF. All SAE will be reported to the EC by the Sponsor in the Annual Safety Report. AESI should be reported to the Sponsor using the eCRF within a maximum of 10 days of awareness.

If safety measures are required, these have to be reported to the EC by the Investigator as well as by the Sponsor within 2 days.

11.3 Follow up of (Serious) Adverse Events

SAEs will be followed until resolution or stabilisation. Participants with ongoing SAEs at study termination will be further followed up until recovery or until stabilisation of the disease after termination.

12. STATISTICAL METHODS

Statistical considerations

12.1 Hypothesis

Null hypothesis A (H_{0A}): ACP Amulet is superior in terms of complete LAA occlusion to WATCHMAN/FLX device and is more feasibility.

Null hypothesis B (H_{0B}): there is no difference between ACP Amulet and WATCHMAN/FLX in terms safety, feasibility and LAA patency.

12.2 Determination of Sample Size

Considering an incidence of the primary composite end-point in the range of 50% in the Watchman/FLX group, which is a conservative estimate based on previous reports, we estimate that 200 patients will provide greater than 80% power to prove superiority of Amulet as compared to Watchman/FLX assuming a 40% risk reduction (i.e. corresponding to an event rate in the range of 30%) and a significance level of 5% (alpha).

12.3 Statistical criteria of termination of trial

No statistical interim analyses are planned.

12.4 Planned Analyses

Datasets to be analysed, analysis populations

The main analysis of the primary endpoint will be conducted on all randomized patients who have completed the 45-day follow-up according to the intention to treat principle, in keeping with the superiority prespecified study hypothesis. Additional analyses of the primary endpoint will be also carried out in the per-protocol and as-treated populations. Similarly, LAA patency and DRT at 45-day and 13-month CCTA and at 45-day TEE **as well as clinical outcomes** will also be analyzed in the per-protocol and as-treated population.

Primary and secondary Analysis

Primary and secondary end points will be analysed on an intention-to-treat basis; as above mentioned some of them will be analysed also in the per-protocol and as-treated populations. Categorical outcome measures will be compared using a χ^2 test or Fisher exact test as required. Continuous variables will be compared using a 2-sided unpaired t test or a Mann-Whitney test, as appropriate. Estimation of the cumulative incidence of safety and efficacy endpoints will be performed using the Kaplan-Meier method, and event rates will be compared by the log rank test. The estimated relative risk (RR) is the ratio of the risk probabilities, and a confidence interval will be constructed based on a logarithmic transformation. Correlations between variables will be analyzed with a Cox regression.

Interim analyses

No statistical interim analyses planned.

Safety analysis

No statistical interim analyses planned.

Deviation(s) from the original statistical plan

Any deviation from the planned analyses will be reported in the final trial report.

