Study Product / Intervention:	
The WATCHMAN (Atritech, Boston Scientific, Natick, MA, USA) LAAC technology consists of the Access System (Access Sheath and Dilator) and Delivery System (Delivery Catheter and WATCHMAN Device). The Access System and Delivery System permit Device placement in the left atrial appendage (LAA) via femoral venous access and inter-atrial septum crossing into the left atrium. WATCHMAN device is a self-expanding nitinol structure with a porous covering on the proximal face. The device is constrained within the Delivery System until deployment in the LAA. The Device is available in 5 sizes from 21 to 33 mm. The new generation Watchman FLX has a shorter device length and a less taper angle to simplify implantation and to fit a wider range of patients. Furthermore, the frame of the new device is designed to enhance sealing within the left atrial appendage.
 
The AMPLATZER Amulet (St. Jude Medical-Abbott) is a self-expanding device made of nitinol that has a distal lobe and a proximal disc, connected by an articulated waist. The device lobe has six to 10 pairs of stabilising wires and is meant to be implanted in the proximal 10-15 mm of the left atrial appendage (LAA), whereas the device disc is intended to cover the ostium at the left atrial side. The proximal female screw is recessed to minimise thrombus formation on the disc and potentially facilitate re-attachment of the device to the pusher screw. The lobe sizes range from 16 to 34 mm.

Number of Participants with Rationale:	
Total number of patients with primary endpoint assessment: 200 100 patients in the Watchman/FLX group 100 patients in the Amplatzer Amulet group Sample size is calculated to state superiority of Amplatzer Amulet compared with Watchman/FLX

Study Duration:	8 years
Study Schedule:	February 2018 February 2026

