8.4 Crossover

In case of impossibility during the procedure to implant the randomized device, operator can choose to implant another device or stop the procedure. In any case the patient will continue to be considered enrolled in the trial. The crossover endpoint will be centrally adjudicated by the Clinical Events Committee (CEC) as justified if there will be evidence that the randomly allocated device has been positioned at least once in the LAA but LAA ostium sealing remained suboptimal (peri-device leak ≥ 3 mm) or concerns were present over the device stability and consequent risk of device embolization.

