12.5 Handling of missing data and drop-outs

Patients with missing data for the primary end-point will be excluded from the primary analysis.

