4.2 Analysis populations

The primary endpoint analysis will be performed using the intention to treat principle on the intention-to-treat, full-analysis set population. Sensitivity analyses will be performed on the per-protocol population. Crossover patients will be considered as a primary end-point event in all analyses.

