4.2.1 Full analysis set (FAS)

The full analysis set (FAS) will include all randomized subjects. Following the intent-to-treat principle, subjects will be analyzed according to the treatment they are assigned to at randomization.

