4.2.2 Per-protocol (PP)

Per-protocol population PP consists of all subjects in the FAS who do not have any major protocol violation. The following items will be considered such a major protocol deviations, which will exclude the patient from the PP (Table 2):

CTU Bern	Swiss APERO SAP	Version: 2.0	
	Template: CS_STA_TEM-11	Valid from: 17.08.2021	

Table 2: Derivation of major protocol violations used for PP definition.

Protocol deviation	eCRF sheet	Variable	Variable type	Derivation of violation
Violation of inclusion or exclusion criteria				
Age ≥ 18 years (ic1)	Baseline	age	Continuous	age<18
Written informed consent (ic2)	Baseline	ic2	Binary: yes/no	no
CHADS2VASC score ≥ 2 (ic5)	Baseline	{score based on baseline variables, add points into score}	Add points	hf=yes (1 point), hypertension=yes (1 point), age ≥ 75 (2 points) OR age 65-74 years (1 point), diabetes=yes (1 point), prior_cerebr=yes OR arterial_embolism=yes OR conc_th=yes (2 points), vasculopathy=yes OR prior_mi=yes OR aortic_plaque=yes (1 point), gender=female (1 point). Violation if score<2
HASBLED ≥ 3 or High bleeding risk HBR as defined by Munich consensus document (ic6)	Baseline	{score based on baseline variables, add points into score}	Add points	HASBLED: uncontroll=yes (1 point), kidney_disease=yes (1 point), liverdisease=yes (1 point), type_cerebr=stroke (1 point), priorbleeding=yes OR anemia=yes OR ind_primary={any of: history of major or minor bleeding, wish to avoid triple therapy, risk of fall, concomitant disease improving bleeding risk ,HASBLED ≥ 3 } (1 point) OR hb ≤ 130 g/L in male/hb <120 g/L in female, inab_oac_variability=3 (1 point), age >65 (1 point), bl_drugs_{oac, noac, aspirin, thienopyridine,fans }=any yes (1 point), alcohol=yes (1 point) HBR: priorbleeding=yes OR anemia=yes OR hb ≤ 130 g/L in male/hb <120 g/L in female Violation if score≤ 2 AND HBR=no
Exclusion criteria not met	Randomization	exclusion_criteria_exclusion_crit	Binary: yes/no	no
First LAAC device used not according to randomization	Procedure	first_device, first_imp_att	Categorical, Number	Equal to randomized but implantation attempts = 0 OR
	Procedure	first_device	Categorical	Unequal to randomized

CHADS2VASC: see <https://www.mdcalc.com/cha2ds2-vasc-score-atrial-fibrillation-stroke-risk>

HASBLED: see <https://www.mdcalc.com/has-bled-score-major-bleeding-risk>

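### Protocol 12.4 limits an intention-to-treat analysis to 45-day completers, dropping adjudicated crossovers who leave early although the SAP counts them; the documents also disagree on whether a stopped procedure is a crossover

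*Combined protocol and SAP*

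**What the plan says.** **Analysis set.** Protocol 12.4 places the main analysis on "all randomized patients who have completed the 45-day follow-up according to the intention to treat principle". Protocol 12.5 adds: "Patients with missing data for the primary end-point will be excluded from the primary analysis". The synopsis sizes the trial to match: "Total number of patients with primary endpoint assessment: 200". The SAP differs. Section 4.2.1 states: "The full analysis set (FAS) will include all randomized subjects". Section 4.2 puts the primary analysis on that set and states: "Crossover patients will be considered as a primary end-point event in all analyses".

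**Crossover.** Protocol 8.4 says that when the allocated device cannot be implanted the "operator can choose to implant another device or stop the procedure", and the patient stays enrolled in either case. The Clinical Events Committee (CEC) accepts a crossover as justified if "the randomly allocated device has been positioned at least once in the LAA but LAA ostium sealing remained suboptimal", or if there were concerns about stability. Protocol 9.1.2 sends a changed device and a stopped procedure alike to crossover adjudication. Protocol 9.2 defines crossover as a switch to the other device.

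**Missing CCTA.** SAP 6.2.3 and 6.4 provide multiple imputation, but only on request. The SAP states no default for patients with neither a crossover nor an evaluable CCTA.

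**The concern.** The composite has two components with different timing. Patency needs a CCTA at 45 days; crossover is settled on the day of the procedure. A completion condition suits the first component but not the second, because it discards patients whose endpoint is already positive. Such patients are known failures of the allocated device, not neutral missing values.

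Two analysts, one following the protocol and one the SAP, could report different numerators and denominators for the primary result. The unsettled crossover wording adds a second source of disagreement, over patients who leave the procedure with no device.

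**Working it through.** **1. The plan's own figure.** Inputs (protocol 12.2, SAP 2.3): 50% versus 30%, 200 patients, 1:1, alpha 5%. Sidedness is not stated; two-sided is assumed.

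Power = Φ{[d − 1.96·√(2·p̄·(1−p̄)/n)] / √[(p₁(1−p₁)+p₂(1−p₂))/n]}, with d = 0.20, p̄ = 0.40, n = 100:

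Φ{[0.20 − 1.96 × 0.0693]/0.0678} = Φ(0.947) = 82.8%.

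The stated power above 80% is reproduced.

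**2. One patient under each rule.** The allocated device is positioned but does not seal, the other device is implanted, the CEC accepts the crossover, and the patient withdraws on day 20.

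| Text | Result |
|---|---|
| Protocol 5.1 | Event, known at implantation |
| Protocol 12.5 | Not excluded: the composite is not missing |
| Protocol 12.4 | Excluded: 45-day follow-up not completed |
| SAP 4.2, 4.2.1 | Included, event |
| SAP 4.2.2, per-protocol | Included, event: Table 2 has no condition on a 45-day visit or CCTA |

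The exclusion comes from the completer condition in 12.4 alone. The per-protocol row is the same protocol-SAP conflict seen again, not a second one.

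**3. A procedure stopped without trying the other device.**

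| Text | Reading |
|---|---|
| Protocol 8.4, 9.1.2 | Goes to crossover adjudication; the criterion needs no second device |
| SAP 1.2, 2.7 | Failed implantation included |
| SAP 3.3, 4.1, 6.2.1 | Only failed cross-over added |
| Synopsis, protocol 5.1 and 9.2, SAP 4.3, 6.1.1, Table 4 footnote (5.7) | Change to the other device only |

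If the CEC adjudicates it as a crossover, the SAP 3.3 composite counts it. If not, there is no attenuation value distal to a device, patency is undefined, and protocol 12.5 excludes the patient even if the 45-day visit takes place. A procedure stopped before the allocated device was positioned does not meet the 8.4 criterion. SAP Table 2 foresees patients with no attempt ("Equal to randomized but implantation attempts = 0") and removes them from the per-protocol set, but no text says how they enter the primary analysis.

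**4. Size.** The documents give no rate for these patients, so the number dropped is an assumption. Drop kW events from Watchman/FLX and kA from Amulet:

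d = (50−kW)/(100−kW) − (30−kA)/(100−kA).

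| kW, kA | Rates | d (points) | Fisher p | Chi-square p |
|---|---|---|---|---|
| 0, 0 | 50/100 vs 30/100 | 20.0 | 0.0059 | 0.0039 |
| 2, 0 | 48/98 vs 30/100 | 19.0 | 0.0087 | 0.0063 |
| 0, 2 | 50/100 vs 28/98 | 21.4 | 0.0023 | 0.0020 |
| 2, 2 | 48/98 vs 28/98 | 20.4 | 0.0052 | 0.0034 |

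Chi-square is uncorrected. If the planned rates are observed, nothing changes. Near the threshold it can: 50/100 vs 37/100 has p = 0.087 (Fisher) and 0.064 (chi-square), and dropping two Amulet events (50/100 vs 35/98) gives 0.046 and 0.042. In the other direction, 50/100 vs 36/100 has chi-square p = 0.046, and dropping two Watchman/FLX events (48/98 vs 36/100) gives 0.065.

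**5. How often.** Take X ~ Bin(100, 0.5) and Y ~ Bin(100, 0.3), enumerate all outcomes, and sum the probability of those where p < 0.05 holds before the drop but not after, or the reverse.

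| Dropped | Change | Fisher | Chi-square |
|---|---|---|---|
| 2 Watchman/FLX | Significance lost | 4.3% | 4.0% |
| 2 Amulet | Significance gained | 7.4% | 4.1% |
| 2 in each arm | Significance gained | 0.36% | 0.21% |

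**The case against.** The best reply is that the SAP has already settled the analysis set. Its version 2.0 header carries the date 17.08.2021, against 29.05.2020 for protocol version 5. It names all randomised subjects and is explicit on crossovers. One trials unit does the analysis (protocol 13.3), outcomes are double-programmed (SAP 6.7), and missed primary assessments are shown by arm (SAP 5.10). Most of this stands: in practice the SAP rule would probably be followed. What remains is an unamended protocol sentence with no stated precedence, and crossover wording that varies within the SAP itself.

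Four stronger readings are tempting and not supported:

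- *Protocol 12.5 alone drops crossovers.* It does not; once crossover is adjudicated the composite is known.
- *SAP Table 1 leaves every device-less patient unclassifiable.* Table 1 derives only patency. The composite in the same section adds adjudicated crossovers, so a case the CEC accepts is still an event.
- *A stopped procedure is already an event.* Protocol 9.1.2 only sends it for adjudication. Rewriting crossover as failure to implant might widen the endpoint.
- *The primary result is materially biased, or biased towards one device.* The documents give neither a count nor a direction. Large one-sided losses, such as five against none, have no basis in them.

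**Conclusion.** The point holds as a conflict that should be fixed. As written, protocol 12.4 is not an intention-to-treat analysis of a composite with a day-0 component, and it contradicts SAP 4.2 and 4.2.1. The status of a procedure stopped without trying the other device is inconsistent across both documents. Excluding other patients without an evaluable CCTA is a clear rule, but it is a complete-case rule and should carry that name.

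The likely effect is small. A changed conclusion needs a result near the threshold and unequal losses: about 4% to 7% of trials if two events are lost from one arm, and under 0.5% if two are lost from each. These figures rest on the planned rates, 100 per arm, a two-sided 5% test and an assumed count of dropped events. Confidence is high on the wording conflict; the size in the actual trial cannot be judged from the documents.

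**What to change.** 1. Amend protocol 12.4 and 12.5 to match SAP 4.2: the primary analysis set is all randomised patients, and an adjudicated crossover is an event whatever the later follow-up or CCTA. Label the exclusion of other patients without an evaluable CCTA as complete-case, and state the same rule in the SAP.
2. Reconcile the crossover wording in the synopsis, protocol 5.1, 8.4, 9.1.2 and 9.2, and SAP 1.2, 2.7, 3.3, 4.1, 4.3, 6.1.1, 6.2.1 and the Table 4 footnote. All should say the same about whether a CEC-adjudicated stopped procedure is an event, including one stopped before the allocated device was positioned. Which answer to adopt is for the sponsor.
3. In SAP 6.2.3 and 6.4, delete the condition that imputation is done only on request, so that this sensitivity analysis of the primary outcome is always reported. Limit it to patients with a device in place and no crossover event, since patency is undefined without a device.

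Cost: text changes, slightly more analysis work, and possibly slightly different event rates. Implantation attempts, aborted procedures and adjudication results are already collected.
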